Three independent individuals with relevant expertise in VTE and anticoagulation will be appointed to a data safety monitoring board (DSMB) whose primary responsibility is to protect the safety of study subjects and to provide ongoing, critical, and unbiased evaluation of the progress of the study. The DSMB will be comprised of two independent physicians and an independent statistician. To further ensure independence of the DSMB, the DSMB Chair has been selected and is an expert in VTE AND comes from outside the Mass General Brigham Network.

The DSMB will:

- Provide independent safety evaluation of events and adjudicate all actual and potential serious adverse events experienced by study subjects during this study
- Review aggregate efficacy and safety data including the frequency of adverse safety outcomes, particularly death, symptomatic VTE and major bleeding; and can recommend premature stopping of the study to the Sponsor and Principal Investigator at any time.

The DSMB will meet virtually via Zoom under the restrictions imposed by the COVID-19 pandemic. The DSMB will meet once before the initiation of the trial and then at least once every three months for the duration of the trial in addition to prespecified meetings at 10 months and 50% of enrollment (Table). In addition, the DSMB may be convened on an *ad hoc* basis at the request of the study investigators if the need (for example, due to a study-related concern) arises in between regularly scheduled meetings. The DSMB chair may call an emergency meeting at any time should questions of patient safety arise or at the request of the Study Safety Monitor. The exact dates and times of the DSMB meetings will be determined based on the availability of all three members to meet and will take place within the first two weeks of the given month.

1. Prior to the first meeting, the DSMB will be provided with FDA- and IRB-approved protocol, DSMB Charter, and DSMB Adjudication Report Form to allow for review and charter revisions prior to the first meeting called the DSMB Kick-off meeting.
2. The DSMB Kick-Off meeting will provide formal training on the protocol provided by the Thrombosis Research Group staff. During the first meeting, the DSMB will review and approve the final Charter. The DSMB will determine reports needed for safety review and establish stopping rules.

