- B. If the study is terminated or suspended, prompt notification will be provided to all parties of the study.
- C. Patient enrollment may be paused or terminated early if the DSMB determines that the potential benefits of continuing the trial are unlikely to outweigh the risks. For example, if the probability of achieving the target primary endpoints falls below a certain threshold, the trial will be stopped or paused for re-evaluation.

2. Safety Stopping Rules

The study will be terminated by the DSMB and principal investigator at any point if the following stopping criterion is met:

- a. An excess of morbidity or mortality is observed in patients receiving apixaban.
- b. When 3 of the subjects receiving apixaban experience an unprovoked intracranial hemorrhage, confirmed by independent adjudication and did not have a protocol violation such that he/she cannot be considered as representative of the intended patient population.
- c. When 3 of the subjects receiving apixaban experience an unprovoked major bleed (including fatal hemorrhagic events) and did not have a protocol violation such that he/she cannot be considered as representative of the intended patient population.

3. Stopping Rules for Futility

The study will be terminated by the DSMB and principal investigator if any of the following stopping criteria is met:

- a. Fewer than 36 events are observed in the placebo group at the time of the 300th patient interim statistical analysis
- b. Enrollment progress has been limited such that the study does not have a reasonable chance of randomizing 600 patients even after efforts to remediate recruitment

Protocol Violations

The study staff will rapidly and firmly address any protocol violations with the DSMB. If a protocol violation is detected or suspected, the investigator(s) will first be asked to provide a written explanation. After reviewing the available information, the study staff will categorize protocol violations as either major (eligibility or

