reduction (75%) in recurrent VTE as low-intensity rivaroxaban (10 mg daily) compared with low-dose aspirin (2). The 75% relative risk reduction was reported specifically for recurrent VTE and in the provoked VTE patient population, comparing rivaroxaban 10 mg daily versus low-dose aspirin. This relative risk reduction specifically pertains to our primary study outcome and our exact patient population and comes from a robust randomized controlled trial analysis. If anything, the reduction in the proposed study should be even greater since we propose a placebo-control instead of active (aspirin) control and we will be following our patients for 12 months, instead of allowing shorter follow-up as was reported in EINSTEIN CHOICE. Accordingly, assuming an estimated incidence in the placebo group of 6% at 12 months and a decrease in the primary outcome of 75% with apixaban 2.5 mg twice daily as compared with placebo, we calculated that we would need to enroll 279 patients in each group for the study to have 80% power to show the superiority of low-intensity apixaban over placebo, at a two-sided alpha level of 0.05. To account for patients who may be lost to follow-up or withdraw from the study, we will recruit 300 in each arm and 600 total.

EINSTEIN-CHOICE enrolled patients after a required 6 to 12 months of anticoagulant therapy. Our study requires that patients complete at least 3 months of anticoagulant therapy in accordance with current and widely-accepted evidence-based clinical practice guidelines (Eur Heart J. 2020; 41: 543–603, Chest. 2016;149:315-352, and Circulation. 2011;123:1788–1830). Data from the PADIS-PE study showed that the rate of VTE recurrence is higher closer in temporal proximity to the initial event, such that the recurrence rate is higher at 3-6 months after diagnosis than it is at 6-12 months (Couturaud F, et al. Six Months vs Extended Oral Anticoagulation After a First Episode of Pulmonary Embolism. JAMA. 2015;314(1):31-40). Accordingly, the anticipated event rate should be higher in our study than EINSTEIN-CHOICE and the resultant observed relative risk reduction is likely to be higher.

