We have conducted a retrospective analysis using an ongoing BWH registry of 405 patients with pulmonary embolism/deep vein thrombosis. We identified 83 patients without active cancer and with at least one provoking risk factor. Among those who received 3-6 months of anticoagulation, 11.1% developed symptomatic recurrent venous thromboembolism in the ensuing year after stopping anticoagulation. If we utilize this baseline rate of recurrent VTE in our sample size calculation, we will require 212 patients in each study group, assuming a 75% relative risk reduction with apixaban 2.5 mg twice daily compared with placebo and 90% power to show the superiority of low-intensity apixaban over placebo, at a two-sided alpha level of 0.05.

We have also consulted with an independent biostatistician from the Harvard Catalyst Biostatistics Program ([name]) to review our sample size requirement. She confirmed our sample size calculation using a recurrent VTE rate in the placebo

group of 6% from the best available literature and also using the rate of 11.1% from our observational cohort of patients that would be eligible for this study (see Table 7. below).

Table 7. Harvard Catalyst Biostatistics Program Consultant Sample Size Calculations (performed by [name] using STATA).

Anticipated Event Rate = 6%	Anticipated Event Rate = 11.1%

. power twoproportions .06 .015, test(chi2) n(558)
 
Estimated power for a two-sample proportions test
 
Pearson's chi-squared test
 
Ho: p2 = p1 versus Ha: p2 != p1
 
Study parameters:
 
 alpha = 0.0500
 
 N per group = 279
 
 p1 = 0.0600
 
 p2 = 0.0150
 
Estimated power: power = 0.8005
 
Required N = 279 per group
	
. power twoproportions .111 .0278, test(chi2) n(424)
 
Estimated power for a two-sample proportions test
 
Pearson's chi-squared test
 
Ho: p2 = p1 versus Ha: p2 != p1
 
Study parameters:
 
 alpha = 0.050
 
 N per group = 212
 
 p1 = 0.1110
 
 p2 = 0.0278
 
Estimated power: power = 0.9236
 
Required N = 212 per group

It was also suggested that we consider using the lower limit of the 95% confidence interval around our estimate of 11.1%, which would be 8.2%. The statistician suggested that this would also provide a conservative estimate of the frequency of recurrent VTE for the sample size calculation (see Table 8 below).

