6.6 Interim Analysis

We will conduct a pre-specified interim analysis to assess the primary safety and efficacy outcomes after 50% of the planned enrollment population has completed 12-month follow-up. This planned interim analysis will inform the Data Safety Monitoring Board on whether the study should be stopped early due to efficacy, safety concerns, or futility or continue to enroll the full 600-patient cohort. The following three elements are used in considering the interim analysis:

6.7 Stopping for safety:

In the event that three distinct occurrences of unprovoked intracranial hemorrhages or major bleeding episodes are observed within the group of patients receiving apixaban, a thorough investigation will be conducted. This investigation will involve a review by an adjudication committee to confirm the authenticity of these incidents, ensuring that there have been no breaches of the study protocol that could have contributed to the adverse events. If the committee determines that these incidents are indeed linked to the apixaban treatment, specific measures will be implemented in response to these findings.

The decision to take action upon the confirmation of three such events is rooted in the clinical expertise of the researchers involved in the study. This threshold was established after extensive deliberation and consultation with the Mass General–Brigham Institutional Review Board (IRB).

The IRB is an independent body responsible for protecting the rights and welfare of human subjects involved in research, and their guidance plays a crucial role in maintaining the ethical standards of the study.

6.8 Stopping for futility:

The futility stopping rule is in place to prevent the unnecessary continuation of a clinical trial if there is a high likelihood that the primary efficacy outcome rate in the placebo arm falls below 6%. This threshold is considered clinically safe and is set to ensure that resources are not wasted on a trial that is unlikely to produce meaningful results. The problem is framed as a hypothesis testing scenario, where the null hypothesis states that the primary efficacy rate is greater than or equal to 0.06, and the alternative hypothesis suggests that it is less than 0.06.

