If the null hypothesis is rejected, it indicates that the actual event rates in the placebo arm are less than 6%. To reject the null hypothesis, fewer than 4 events must be observed. In this context, the trial's progress will be assessed during an interim statistical analysis when the 12-month follow-up is completed for the 300th patient. At this point, if there are fewer than 4 events observed in the placebo group, the decision to terminate the trial will be considered.

6.9 Stopping for efficacy (superiority):

The efficacy stopping rule is a guideline used to determine whether a clinical trial should be terminated early based on the observed results. This rule is applied in situations where the data collected from the trial's participants, in this case, 300 patients, clearly demonstrates that the treatment being studied has a significantly higher efficacy than the placebo. The objective is to avoid exposing more patients to an inferior treatment (placebo) and to expedite the process of bringing a highly effective treatment to the market.

In this specific scenario, the efficacy stopping rule is based on the unadjusted hazard ratio, which is a measure of the relative risk of an event occurring in the treatment group compared to the placebo group. A hazard ratio of less than 0.1 is considered as "overwhelmingly superior efficacy," indicating that the treatment group has a much lower risk of the event than the placebo group.

To determine whether the trial should be stopped, a hypothesis test is conducted. The null hypothesis (H_0) states that the hazard ratio is larger than or equal to 0.1, while the alternative hypothesis (H_1) states that the hazard ratio is smaller than 0.1. If the null hypothesis is rejected based on the data collected from the enrolled patients, it would be concluded that the treatment has overwhelmingly superior efficacy compared to the placebo. As a result, the trial would be terminated early, allowing for a more rapid progression towards making the effective treatment available to patients who could benefit from it.

References

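### The final protocol's futility trigger of fewer than 36 placebo events at the 300-patient interim is met almost surely at the design rate of 6%, and it conflicts with the SAP's bound of fewer than 4 for the same look

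*Combined protocol and SAP*

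**What the plan says.** Both protocol versions carry the same futility rule under Stopping Criteria, item 3. The lead-in is mandatory: "The study will be terminated by the DSMB and principal investigator if any of the following stopping criteria is met". The first criterion is "Fewer than 36 events are observed in the placebo group at the time of the 300th patient interim statistical analysis". The Interim Safety and Efficacy Analysis section defines the look as the first 300 enrolled patients once they have 12 months of follow-up.

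The sample size is built on "assuming an estimated incidence in the placebo group of 6% at 12 months", a 75% relative reduction and 1:1 allocation. The same section also reports a local registry in which "11.1% developed symptomatic recurrent venous thromboembolism in the ensuing year after stopping anticoagulation".

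SAP 6.8 frames futility at the same look as a one-sided test in which "the null hypothesis states that the primary efficacy rate is greater than or equal to 0.06". Its bound is: "To reject the null hypothesis, fewer than 4 events must be observed". Its consequence is softer: "if there are fewer than 4 events observed in the placebo group, the decision to terminate the trial will be considered". No test level or method is given.

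The amendment table between the two protocol versions has one entry, the COVID-19 inclusion note. The final protocol is dated 11/19/2021 and the SAP 03/24/2025. Neither gives the date of the interim look.

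**The concern.** A futility rule should stop a trial that is unlikely to answer its question and leave alone one that is performing as designed. The protocol's count equals the design rate applied to all 600 patients (0.06 × 600 = 36), yet it is applied to the placebo half of the first 300. That origin is an inference, since the documents show no derivation, and the finding does not depend on it.

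The number is worded as binding, and a second number for the same look, ninefold smaller, sits in the SAP with different force. An outside reader cannot tell which rule was pre-specified when the DSMB met. Continuing with, say, 9 placebo events would breach the protocol and comply with the SAP.

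**Working it through.** **Inputs.** Placebo rate 6% and relative reduction 75% (protocol, Sample Size Calculation); other cited rates 8.8% (placebo arm of the earlier apixaban extension trial, same section) and 11.1% (local registry). Placebo patients at the look: 300 × ½ = 150, from 1:1 allocation. Events are taken to be primary-outcome VTE; the protocol rule does not name the type, but the DSMB duties and SAP 6.8 point to it.

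**The plan's own sample size.** A two-sided 0.05 test of 0.06 against 0.015 at 80% power, without continuity correction, needs 279 per group, and power at 279 is 0.8005. Both match the protocol, so 6% is the operative design rate.

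**Can 36 be recovered as a placebo count?**
- Placebo at the interim: 150 × 0.06 = 9
- Both arms at the interim: 9 + 150 × 0.015 = 11.25
- Placebo in the whole trial: 300 × 0.06 = 18
- Both arms in the whole trial: 18 + 300 × 0.015 = 22.5

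None gives 36. As a rate, 36/150 = 24%.

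**Probability that the protocol rule is met**, X ~ Binomial(150, p), P(X ≤ 35):

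| p | Expected events | P(fewer than 36) |
|---|---|---|
| 6% | 9.0 | 1 − 6.7 × 10⁻¹³ |
| 8.8% | 13.2 | 1 − 2.4 × 10⁻⁸ |
| 11.1% | 16.7 | 0.99999 |
| 20% | 30.0 | 0.87 |

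The probability falls to one half only at p = 23.7%.

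**More generous counting.** Suppose every placebo patient enrolled by the look contributes. Assume uniform accrual of 600 over 20 months, the look at month 22, follow-up capped at 12 months and a constant hazard. Then 14.3 events are expected at 6%, and P(fewer than 36) is 1 − 4.2 × 10⁻⁷ at 6%, 0.999 at 8.8% and 0.96 at 11.1%. With all 300 placebo patients fully followed, which is not the interim data set, it is 0.99993 at 6%, 0.96 at 8.8% and 0.66 at 11.1%.

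**The SAP bound**, X ~ Binomial(150, p), P(X ≤ 3): 0.019 at 6%, 0.146 at 4%, 0.338 at 3%.

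**Disagreement.** Any placebo count from 4 to 35 triggers the protocol rule but not the SAP rule. At 6%, P(4 ≤ X ≤ 35) = 1 − 0.0186 − 6.7 × 10⁻¹³ ≈ 0.981.

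**Level behind the SAP bound.** At 6% and n = 150, P(X ≤ 3) = 0.0186 and P(X ≤ 4) = 0.0499. An exact one-sided 0.025 test therefore gives fewer than 4, and an exact 0.05 test just admits fewer than 5. At n = 149, P(X ≤ 4) = 0.0519, so the 0.05 test also gives fewer than 4. At n = 143, P(X ≤ 3) = 0.0252, so the 0.025 test drops to fewer than 3. A Poisson calculation with mean 9 gives 0.021 at 3 events and 0.055 at 4, hence fewer than 4 at either level. The bound does not reveal its level, and it shifts with small changes in the placebo count.

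**The case against.** **The DSMB is advisory.** The protocol says that "The DSMB will determine reports needed for safety review and establish stopping rules", asks the board to weigh efficacy events first, and lists its actions as recommendations. This softens the practical consequence, and nothing shows that the 36 was ever applied. But the first listed recommendation is termination when the futility criteria are met, which leads back to the 36. Discretion also cannot make a trigger informative when it is practically always met.

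**The later SAP corrects the number.** It may have been meant to, but it does not say so, and no text gives it precedence over the protocol.

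**Enrichment could raise the rate.** The protocol mentions multipliers of 2 to 4, and 4 × 6% = 24%. Even so, the design rate was kept at 6%, and no stated 12-month rate exceeds 11.1%.

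**The SAP bound is lenient.** This stands as a caution. At a true placebo rate of 3% it lets the trial continue about two times in three (1 − 0.338 = 0.662), although the protocol's Table 5 asks for 1140 patients at that rate. Adopting the SAP number removes the contradiction but does not itself justify the number.

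**The look may be past.** This also stands. On the planned timeline it would have preceded the SAP. An amendment would then not be prospective, and the remedy must allow for that.

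**Conclusion.** The point holds and must be fixed. As written, the protocol trigger is met with near certainty at the design rate and at every 12-month rate the sample-size section cites. It conflicts with the SAP in number (36 against 4) and in force (mandatory against discretionary), and nothing reconciles the two.

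The conclusion rests on about 150 placebo patients at the look and on events meaning primary VTE. At 6% it is insensitive to the first assumption, since even 300 placebo patients leave the trigger practically certain. The DSMB charter is not among the documents and might show which rule the board used.

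**What to change.** By dated protocol amendment, withdraw the 36-event criterion and align the protocol with SAP 6.8: fewer than 4 events among about 150 placebo patients with 12-month follow-up, with VTE named as the event. Use the same wording for the consequence in both documents, and check the DSMB charter against it. In SAP 6.8, state the test level, the method, and how the bound is recomputed if the placebo count is not 150.

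State whether the amendment precedes the interim look. If the look has taken place, do not present the new bound as prospective; record which bound the DSMB applied and when it was adopted.

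Cost: one amendment with IRB approval (the COVID-19 clarification also carried an approval date), one or two sentences in the SAP, and a charter check.

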Table. 8 Harvard Catalyst Biostatistics Program Consultant Sample Size Calculation Using Lower Limit of 95% Confidence Interval of Our Observational Cohort Estimate (performed by [name] using STATA).

Anticipated Event Rate = 8.2%

. power twoproportions .082 .0205, test(chi2) n(558)
 
Estimated power for a two-sample proportions test
 
Pearson's chi-squared test
 
Ho: p2 = p1 versus Ha: p2 != p1
 
Study parameters:
 
 alpha = 0.0500
 
 N = 558
 
 N per group = 279
 
 p1 = 0.0820
 
 p2 = 0.0205
 
Estimated power: power = 0.9111
 
Required N = 279 per group

Using this more conservative sample size calculation, we would aim to enroll 300 patients in each arm for a total trial population of 600.

Statistical Analysis Plan

For this study, we will calculate:

- 1) the 12-month frequency of major and clinically relevant non-major bleeding
- 2) the 12-month frequency of symptomatic recurrent VTE

The primary efficacy objective of this trial is to determine whether apixaban 2.5 mg twice daily is superior to placebo for the primary endpoint of symptomatic, recurrent VTE after 12 months of extended therapy. The analysis will include descriptive statistics of event rates and 95% CI, and risk difference and 95% CI. The Mantel-Haenszel statistic will be used to test this hypothesis formally. Superiority over placebo will be claimed for a dose if the Hochberg adjusted p-value is ≤ 0.05 and the RR is < 1 . The analysis will be supported by Kaplan-Meier curves. The primary efficacy outcome analysis will be intention-to-treat. We will also perform an on-treatment analysis.

The primary safety objective will be to determine whether apixaban 2.5 mg twice daily results in a statistically significant difference in major bleeding at 12 months (during the treatment period) compared with placebo. Analysis of incidence of these endpoints will be based on the safety analysis set. The analysis will include descriptive statistics of event rates and 95% CI, and risk difference and 95% CI. Hypotheses will be tested using Mantel-Haenszel statistic. The analysis will be supported by Kaplan-Meier curves of the time to first adjudicated major bleeding event. All bleeding analyses will be conducted on the safety dataset.

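### The 8.2% lower confidence limit in the protocol's sample size section, and the 91% power built on it, cannot come from a subset of at most 83 patients

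*Combined protocol and SAP*

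**What the plan says.** All of this is in the protocol under Statistical Methods, Sample Size Calculation, with the same text in the August 2020 and November 2021 versions.

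- The main calculation assumes 6% recurrence on placebo and a 75% reduction: "we calculated that we would need to enroll 279 patients in each group for the study to have 80% power". Allowing for losses, "we will recruit 300 in each arm and 600 total".
- Local data are then brought in from an "ongoing BWH registry of 405 patients with pulmonary embolism/deep vein thrombosis". The protocol first narrows this registry: "We identified 83 patients without active cancer and with at least one provoking risk factor". It then reports the recurrence rate for only a part of that smaller group: "Among those who received 3-6 months of anticoagulation, 11.1% developed symptomatic recurrent venous thromboembolism", counted over the year once treatment had ended. The size of that last group and its number of events are not given.
- An independent biostatistician is reported to have suggested "using the lower limit of the 95% confidence interval around our estimate of 11.1%, which would be 8.2" per cent, described as conservative.
- The consultant's Table 8 enters 0.082 against 0.0205 with 279 per group and returns "Estimated power: power = 0.9111".
- The text below the table draws the conclusion: "Using this more conservative sample size calculation, we would aim to enroll 300 patients in each arm".

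**The concern.** The text narrows 405 patients to 83, and then to those of the 83 who had 3 to 6 months of anticoagulation. A proportion of 11.1% on so few patients has a wide interval, yet the stated lower limit is only 2.9 percentage points below the estimate (11.1 − 8.2).

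Table 8 is there to show that a pessimistic reading of the site's own data still leaves more than 90% power. If the limit is too high, that reassurance fails: the local data give no margin over the 6% assumption. The closing sentence also presents the enrolment target as resting on this calculation.

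**Working it through.** **Inputs.** Registry 405; eligible subset 83; rate 11.1%; stated lower limit 8.2%; 75% relative reduction; 279 per group; two-sided alpha 0.05; Pearson chi-squared test. All are from the Sample Size Calculation section.

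**Step 1: reproduce the protocol's power figures.** With p2 = 0.25 × p1 and p̄ = (p1 + p2)/2,

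power = Φ{ [ |p1 − p2|·√n − 1.96·√(2p̄(1 − p̄)) ] / √(p1(1 − p1) + p2(1 − p2)) }.

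- 6% v 1.5%, n = 279: (0.7516 − 0.5266)/0.2668 = 0.844, so power is 0.8005, as stated.
- 8.2% v 2.05%, n = 279: (1.0273 − 0.6112)/0.3088 = 1.347, so power is 0.9111, as stated.

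Table 8 is therefore computed correctly from its input. The question is the input.

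**Step 2: which counts are possible?** With a denominator of 83 or less, the only fractions that round to 11.1% are 1/9, 2/18, and so on up to 9/81. For each method the lower limit is highest at 9/81.

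**Step 3: lower 95% limit for 9/81.**

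- Wald: 0.1111 − 1.96·√(0.1111 × 0.8889/81) = 0.1111 − 0.0684 = 4.27%.
- Wilson, with z² = 3.84: [0.1111 + z²/162 − 1.96·√(0.1111 × 0.8889/81 + z²/(4 × 81²))] / (1 + z²/81) = (0.1348 − 0.0724)/1.0474 = 5.96%.
- Exact (Clopper-Pearson): 2.5% point of Beta(9, 73) = 5.21%.
- Jeffreys 5.64%; Agresti-Coull 5.75%; log-scale 6.00%.

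A two-sided 90% interval does not reach 8.2% either: 5.4% (Wald), 5.9% (exact), 6.6% (Wilson).

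**Step 4: denominators that would give 8.2%.** These are the denominators for which the rate rounds to 11.1% and the lower limit rounds to 8.2%: Wilson 323–361, exact 386–425, Wald 431–470. The minima are about four to five times 83 (323/83 = 3.9; 431/83 = 5.2).

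**Step 5: power on the attainable limits, 75% reduction.**

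| Method (9/81) | Lower limit | Power, 279 per arm | Power, 300 per arm | N per arm for 80% |
|---|---|---|---|---|
| Wald | 4.27% | 65% | 68% | 397 |
| Exact | 5.21% | 74% | 77% | 323 |
| Wilson | 5.96% | 80% | 83% | 281 |
| As stated in Table 8 | 8.2% | 91% | 93% | 201 |

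The first three rows are upper bounds for their methods, because the true subset may be smaller than 81. If it were 5/45 (an assumption for illustration), the exact limit would be 3.7% and power at 279 per arm 59%.

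**A possible origin.** The exact limit for 45/405 is 8.22%, which would match if the whole registry had been used as the denominator. The documents do not say so, and the conclusion does not depend on it.

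**The case against.** The strongest objection is that nothing in the design depends on 8.2%. The 279 and the 300 per arm are derived from the 6% rate before the registry is mentioned. Table 8 fixes the total at 558 and only reports power. SAP section 6.1 uses 6% and a 75% reduction, and SAP section 6.8 frames futility around 6%; neither uses 8.2%. Table 5 already shows that 848 patients are needed at 4% and 1140 at 3%, so the sensitivity to a low placebo rate is disclosed. All of this stands, and it limits the matter to a wrong supporting figure.

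A second objection is that the denominator is not stated, and 11.1% may have been taken from a wider part of the registry. In that case 8.2% could be right for that group. But the description of the cohort would then be wrong, since the protocol presents the 11.1% as coming from patients who would be eligible for this study. The limit would also not speak for the eligible patients.

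A third is that the sentence leading to 300 per arm is merely loose. Perhaps so, but it names this calculation as the basis and calls it more conservative. A placebo rate of 8.2% is less conservative than 6%: Table 5 requires 412 patients at 8% and 558 at 6%.

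**Conclusion.** The point holds. On the stated subset, the lower 95% limit around 11.1% is about 6% at most and may be close to 4%, not 8.2%. The matching power at 279 per arm is about 65% to 80%, depending on the interval method, not 91%. This assumes that the 11.1% was calculated within the 83 patients, as the text reads, and takes the most favourable count possible (9/81). The primary sample size calculation reproduces and is unaffected. The error lies in a supporting confidence limit and in the power derived from it, which the protocol presents as an independent statistician's calculation.

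**What to change.** 1. State the number of events and the number of patients behind 11.1%.
2. Recompute the lower limit on that subset, name the interval method, and restate Table 8 with that limit (about 6% or less if the subset lies within the 83) and its power (about 80% at best with 279 per arm). Alternatively, delete Table 8. If 11.1% proves to come from a wider group, correct the description of the cohort and say that the limit does not apply to the eligible patients.
3. Delete the sentence that ties 300 per arm to this calculation, and rest the 600 on the 6% calculation plus the allowance for losses.

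The cost is protocol wording, and a supporting power figure that becomes less favourable or disappears. The sample size and the SAP do not change.
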